3.2 PRIMARY ENDPOINT(S) ANALYSIS

3.2.1 Definition of endpoint(s)

The primary endpoint is confirmed objective response determined according to RECIST v1.1. A confirmed objective response is defined as a confirmed CR or PR as best overall response (BOR). The BOR will be derived according to RECIST v1.1 definitions (1, 2) based on the Investigator's assessment. The BOR is the best overall response observed from the date of the first administration of IMP until documented disease progression, death, start of an anticancer therapy, or analysis cut-off date, whichever occurs first.

3.2.2 Main analytical approach

The primary analysis will be based on a primary estimand introduced in Section 1.2.1. It is defined according to the following attributes:

- The primary endpoint is confirmed objective response (confirmed CR or PR as BOR) as per RECIST v1.1 .
- The treatment condition of interest is tusamitamab ravtansine.
- The analysis population is the all-treated population (defined in Section 2).
- Intercurrent events:
 - The study intervention discontinuation intercurrent event will be handled with the treatment policy strategy. Confirmed objective response will be assessed based on tumor assessments regardless of study intervention discontinuation.
 - The further anticancer therapy (including further systemic anticancer therapies) intercurrent event will be handled with the "while not initiating further anticancer therapy" strategy. Confirmed objective response will be assessed based on tumor assessments done up to the time of initiation of further anticancer therapy.
- The population-level summary will be the ORR, defined as the rate of participants with confirmed objective response and two-sided 95% CI using the Clopper-Pearson method.

In the absence of confirmed objective response before the analysis cut-off date (taking into account the intercurrent event handling strategies), participants will be considered as non-responders, whatever the reason (including participants with non-evaluable BOR).

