- Activity population: All-treated participants who have measurable disease at study entry and at least 1 postbaseline evaluable tumor assessment. Participants with no postbaseline evaluable tumor assessment but with an early clinical progression or who died from disease progression will also be included in this set. This population is the secondary population for analysis of efficacy parameters.
- **Pharmacokinetic population:** All participants from the all-treated population with at least 1 postbaseline PK concentration with adequate documentation of dosing and sampling dates and times.
- Anti-therapeutic antibodies (ATA) population: All participants from the all-treated population with at least 1 postbaseline ATA result (negative, positive, or inconclusive).

• Analysis of primary endpoint:

- Objective response rate (ORR) will be summarized for the all-treated population using descriptive statistics and 95% exact CI will be provided using the Clopper-Pearson method. As a supplementary analysis, ORR will also be summarized on the activity population.

• Analysis of secondary efficacy endpoints:

- Duration of response (DOR) will be summarized for the subgroup of participants who achieved confirmed objective response for the all-treated population with descriptive statistics using Kaplan-Meier methods. The median DOR and associated 95% CI will be provided,
- Progression-free survival (PFS) will be summarized for the all-treated population using Kaplan-Meier methods. The median PFS and associated 95% CI will be provided, along with probabilities of being progression-free at different time points,
- Disease control rate (DCR) will be summarized for the all-treated population using descriptive statistics and 95% CI will be provided using the Clopper-Pearson method. As a supplementary analysis, DCR will also be summarized on the activity population.

• Analysis of safety endpoints:

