9.4 SAMPLE SIZE DETERMINATION

Assuming a pre-screening failure rate of 84% and a study screening failure rate of 15%, approximately 285 participants will be pre-screened to achieve approximately 38 treated participants in the study.

The initial plan is to treat a total of 38 participants evaluable for anti-tumor activity (at least 1 postbaseline tumor assessment, early clinical progression, or death due to disease progression).

Estimated ORR and 95% exact CIs by number of responders from a sample size of 38 evaluable participants for anti-tumor activity are listed in Table 8.

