3 STATISTICAL ANALYSES

3.1 GENERAL CONSIDERATIONS

This study is not intended to explicitly test a hypothesis. For the primary and secondary efficacy endpoints, 95% CIs will be provided.

All efficacy endpoints based on radiological assessments of tumor burden (ie, ORR, DOR, PFS, and DCR) will be derived using the local radiologist's/Investigator's assessment.

In general, continuous data will be summarized using the number of observations available, mean, standard deviation, median, Q1, Q3, minimum, and maximum. Categorical and ordinal data will be summarized using the count and percentage of participants.

The baseline value is defined as the last available value before the first dose of IMP.

The study cut-off for analysis of the primary endpoint, ORR, corresponds to the date on which all evaluable treated participants have had at least 2 postbaseline tumor assessments, experienced confirmed objective response, or have discontinued the study treatment for any reason. For participants with 2 postbaseline tumor assessments and occurrence of response at the second postbaseline tumor assessment, it will also include the confirmatory assessment. This study cut-off can be up to approximately 20 weeks (16 weeks for 2 tumor assessments and 4 weeks for confirmation of response, if needed) after the last participant's first IMP administration. Of note, DCR will also be assessed at this cut-off.

The final study cut-off for analysis of the secondary efficacy endpoints, which include DOR and PFS, will be 4 months after the cut-off date for the primary analysis. At that time, the primary analysis of ORR and DCR will also be updated.

Observation period

The observation period will be divided into 4 segments:

- The **pre-treatment period** is defined as the period up to first IMP administration.
 - The **pre-screening period** is defined as the period from the pre-screening informed consent to the day before the screening informed consent.
 - The **screening period** is defined as the period from the screening informed consent up to the first IMP administration.
- The **on-treatment period** (ie, treatment-emergent period) is defined as the period from the first IMP administration to 30 days after the last IMP administration.
- The **post-treatment period** is defined as the period from the end of the on-treatment period.

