3.8 INTERIM ANALYSES

An interim analysis for futility based on the number of confirmed objective responses observed in the activity population will be performed.

The study cut-off date for the interim analysis corresponds to the date on which the first 20 evaluable treated participants have had at least 2 postbaseline tumor assessments, experienced confirmed objective response, or have discontinued the study for any reason. For participants with 2 postbaseline tumor assessments and occurrence of response at the second postbaseline tumor assessment, the confirmatory assessment will also be included.

If 0 or 1 confirmed objective response is observed among the first 20 treated participants evaluable for anti-tumor activity, the enrollment will be stopped. Otherwise, the enrollment will continue with the 18 additional evaluable participants.

The study analysis will then be conducted in 2 steps.

The first step analysis will be conducted when all evaluable treated participants have had at least 2 postbaseline tumor assessments, experienced confirmed objective response, or have discontinued the study treatment for any reason. This study cut off can be up to approximately 20 weeks (16 weeks for 2 tumor assessments and 4 weeks for confirmation of response, if needed) after the last participant's first IMP administration. Of note, DCR will also be assessed at this cut-off.

The second step analysis for analysis of the secondary efficacy endpoints will be conducted approximately 4 months after the cut-off date for the primary analysis. At that time, the primary analysis for ORR and DCR will also be updated.

The final analysis will be conducted at the end of the study. Only safety analyses will be updated at this time.

For each analysis step, the analysis cut-off date will be defined as the date of the database extraction that will be performed for the analysis after the cut-off (study cut-off for the interim analysis, as well as the first and second analysis steps).

Analyses methods and conventions described in the other sections of this SAP will be applied for all analyses as applicable. The following additional rules will apply for analyses performed at interim analysis and at first analysis step:

- Participants without end of treatment visit performed at the time of the cut-off date will be considered as ongoing and exposed up to the cut-off date. Therefore:

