4 SAMPLE SIZE DETERMINATION

Assuming a pre-screening failure rate of 84% and a study screening failure rate of 15%, approximately 285 participants will be pre-screened to achieve approximately 38 treated participants in the study.

The initial plan is to treat a total of 38 participants evaluable for anti-tumor activity (at least 1 postbaseline tumor assessment, early clinical progression, or death due to disease progression).

Estimated ORR and 95% exact CIs by number of responders from a sample size of 38 evaluable participants for anti-tumor activity are listed in Table 7.

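### The ORR confidence interval is a fixed-sample Clopper-Pearson interval that ignores the 0-1/20 futility stop, so its upper limit is too low when the trial continues and ends with about 2 to 5 responders

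*SAP*

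**What the plan says.** **Interval.** SAP 3.2.2 makes the primary summary the "rate of participants with confirmed objective response and two-sided 95% CI using the Clopper-Pearson method", in the all-treated population. Protocol 9.2.2 specifies the same method. The Protocol synopsis says that a "95% exact CI will be provided using the Clopper-Pearson method". SAP 3.2.4 repeats the approach in the activity population as a supplementary analysis, and SAP 3.2.3 plans no sensitivity analysis.

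**Stopping rule.** SAP 3.8 (likewise Protocol 9.3) plans a look for futility, counted in the activity population: "If 0 or 1 confirmed objective response is observed among the first 20 treated participants evaluable for anti-tumor activity, the enrollment will be stopped". With 2 or more responses at that look, recruitment goes on until 18 more have been added, 38 evaluable in all.

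**Precision.** SAP 4 announces a table: "Estimated ORR and 95% exact CIs by number of responders from a sample size of 38 evaluable" participants. Protocol 9.4 has the same sentence. The table bodies are not in the text supplied, and neither section names the interval method.

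**Purpose.** Protocol 9 and SAP 3.1 say that no hypothesis is explicitly tested. Protocol 9 adds that power and Type I error were not considered in the design. SAP 3.1 says: "For the primary and secondary efficacy endpoints, 95% CIs will be provided".

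No section of either document adjusts the ORR estimate or its interval for the interim stop.

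**The concern.** Clopper-Pearson limits at most 2.5% error to each tail when the number of participants is fixed in advance. In this trial it is 20 or 38, depending on the first 20 results. A result of x/38 can occur only if the first 20 gave at least 2 responses. When the upper limit for a low x/38 is derived, the outcomes at least as unfavourable include 0/20 and 1/20. The single-sample calculation replaces them with outcomes such as 1/38, which the design cannot produce, and gives them too little probability.

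One symptom needs no theory. Under the plan, 1/20 fails the interim and has an upper limit of 24.9%, while 2/38 passes it and has an upper limit of 17.7%. Passing the futility look would seem to rule out more activity than failing it.

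With no hypothesis test, the interval is the plan's statement of uncertainty about its primary endpoint. An interval called exact should have the coverage that the word promises.

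**Working it through.** **Inputs.** First stage n1 = 20, stop at 0 or 1, second stage n2 = 18 (SAP 3.8, Protocol 9.3); two-sided 95%, so 0.025 per tail (SAP 3.1, 3.2.2).

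**The plan's own figure.** The visible sample-size figure is 285 pre-screened for about 38 treated. 285 × 0.16 × 0.85 = 38.8, so it reproduces. The precision table cannot be checked.

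**Planned limits.** For x responders in n, the lower limit is the 0.025 quantile of Beta(x, n−x+1) and the upper limit is the 0.975 quantile of Beta(x+1, n−x).

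**Two-stage exact limits.** The possible outcomes are ordered 0/20, 1/20, 2/38, 3/38 and so on. Stage-wise ordering and ordering by observed rate give the same sequence. For true rate p:

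- P(0/20) = (1−p)^20 and P(1/20) = 20p(1−p)^19.
- P(t/38) = Σ over x = 2, 3, … of Bin(x; 20, p) × Bin(t−x; 18, p).
- The upper limit solves P(this outcome or one earlier in the order) = 0.025. The lower limit solves P(this outcome or one later) = 0.025.

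Example, upper limit at 2/38. A single sample needs P(X ≤ 2 | n = 38) = 0.025, which gives p = 17.75%. The two-stage design needs P(0/20) + P(1/20) + P(2/38) = 0.025. At p = 24.94% the terms are 0.0032 + 0.0214 + 0.0004 = 0.0250.

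| Outcome | Planned 95% CI (%) | Two-stage exact 95% CI (%) | Upper limit too low by (points) |
|---|---|---|---|
| 0/20 | 0.00–16.84 | 0.00–16.84 | 0 |
| 1/20 | 0.13–24.87 | 0.13–24.87 | 0 |
| 2/38 | 0.64–17.75 | 1.23–24.94 | 7.2 |
| 3/38 | 1.66–21.38 | 2.06–25.43 | 4.1 |
| 4/38 | 2.94–24.80 | 3.20–26.79 | 2.0 |
| 5/38 | 4.41–28.09 | 4.57–28.97 | 0.9 |
| 6/38 | 6.02–31.25 | 6.11–31.62 | 0.4 |
| 8/38 | 9.55–37.32 | 9.57–37.37 | 0.05 |

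The two-stage limits remove the reversal: 24.87% at 1/20, then 24.94% at 2/38. The planned lower limits are slightly below the two-stage ones, so they err on the cautious side.

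**Coverage of the planned interval.** For each p, add the probabilities of the outcomes whose planned interval misses p. This check does not depend on any ordering.

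| True ORR | Upper limit below p | Lower limit above p | Coverage |
|---|---|---|---|
| 5% | 0% | 1.0% | 99.0% |
| 10% | 0% | 1.1% | 98.9% |
| 15% | 0% | 2.1% | 97.9% |
| 20.3% | 1.3% | 1.4% | 97.3% |
| 24.9% | 4.1% | 1.5% | 94.4% (lowest) |
| 30% | 1.9% | 1.8% | 96.3% |

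At 24.9%, the outcomes with upper limits below p are 0/20, 1/20, 2/38, 3/38 and 4/38: 0.0033 + 0.0217 + 0.0004 + 0.0032 + 0.0124 = 0.041. Two-sided coverage is below 95% only for true rates of about 24.9–26.3% and 28.1–28.6%.

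**How often the affected counts occur.** Among trials that continue, 2 to 5 responders is the final count in 73% at a true ORR of 10% and in 40% at 15%.

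**The case against.** The strongest reply is that the trial seeks a signal and tests nothing. The only decision rule is the count at 20, which the interval does not affect. The loss of coverage is at most 0.6 point and confined to two narrow bands of true rate. At 5% to 20% the planned interval covers more often than 95%. Its lower limits, which guard against claiming activity falsely, are conservative. All of this stands, and it limits the weight of the point. It does not make the interval exact, and it does not explain why 2/38 should have a lower upper limit than 1/20.

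A reader might infer that a result of 2/38 would wrongly rule out the 20.3% ORR of the earlier high-expression cohort. The documents do not support that. Protocol 2.1 and 4.3 report 20.3% as background, and nothing makes it a null, target or threshold here. At a true rate of 20.3% the upper limit falls short 1.3% of the time, within the nominal 2.5%, and 2/38 has probability 0.2%. It is true that the planned interval at 2/38 leaves out 20.3% and the two-stage interval keeps it, but that compares two methods at one rare outcome.

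Two further objections stand and shape the fix. The stop is counted in the activity population, whereas the primary ORR uses all treated participants, whose number may exceed 38; a 20+18 calculation therefore does not transfer directly to the primary analysis. And the method behind the precision tables is only inferred from the word exact.

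**Conclusion.** The point holds in a limited form. The planned ORR interval is not exact under the planned stopping rule. After continuation its upper limit is too low by 7.2, 4.1, 2.0 and 0.9 points at 2, 3, 4 and 5 responders of 38, and by 0.4 point or less from 6. The worst case over true rates is 94.4% coverage with 4.1% upper-side error. It is not a general failure of the interval, it is not undercoverage at low response rates, and it alters no planned decision.

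The figures assume stages of exactly 20 and 18 evaluable participants, the rule applied as written, and an early stop analysed on those 20. The point-by-point differences also assume the ordering given above; the coverage figures do not. Participants treated beyond the first 20 before the interim result is known, or a different all-treated denominator, would move the numbers.

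**What to change.** 1. In SAP 3.2.2 and 3.2.4 and Protocol 9.2.2: when the trial continues past the interim, report the two-stage exact 95% CI for ORR in the activity population, where the stopping rule is defined. Use the realised stage sizes and state the outcome ordering.
2. Keep the all-treated Clopper-Pearson interval as planned, labelled as not adjusted for the interim stop. Amend the description in the Protocol synopsis to match.
3. If Protocol Table 8 and SAP Table 7 use single-stage limits, show the two-stage limits for 2 or more responders.

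A bias-adjusted estimate (UMVUE) and a table of early-stop probabilities by true ORR would be optional additions.

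The cost is a few lines of SAP text and code, and wider upper limits at 2 to 5 responders. No extra participants or data are needed.

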3.2.3 Sensitivity analysis

No sensitivity analysis is planned in this study.

3.2.4 Supplementary analyses

The number (%) of participants within each BOR category, including not evaluable as per RECIST 1.1 and reason for being not evaluable will be provided for the all-treated population.

As a supplementary analysis, ORR as per RECIST v1.1 will also be summarized on the activity population (defined in Section 2). The same analytical approach as for the primary analysis defined in Section 3.2.2 will be used.

In addition, the best relative tumor change from baseline, defined as the smallest relative tumor change from baseline (where tumor change at time t is the difference between sum of the longest diameters of the target lesions at time t and baseline), will be summarized using a waterfall plot on the activity population (defined in Section 2).

3.3 SECONDARY ENDPOINT(S) ANALYSIS

The secondary endpoints detailed in this section are progression-free survival, disease control rate and duration of response. Other secondary endpoints analyses are defined in Section 3.6.2 (AE, SAE), Section 3.6.3 (laboratory abnormalities), Section 3.7.1.1 (PK) and Section 3.7.1.2 (immunogenicity).

3.3.1 Key/Confirmatory secondary endpoint(s)

There are no key/confirmatory secondary endpoints.

3.3.2 Supportive secondary endpoint(s)

3.3.2.1 Definition of endpoints

3.3.2.1.1 Progression-free survival

PFS is defined as the time from the date of the first administration of IMP to the date of the first documentation of objective PD according to RECIST v1.1 (1, 2) or death due to any cause, whichever comes first.

The analysis of PFS will be based on the following censoring rules:

- If documented disease progression or death is not observed before the analysis cut-off date, then PFS will be censored at the date of the last evaluable tumor assessment performed before the analysis cut-off date.
- A participant without PFS event (documented disease progression or death) and without any evaluable post-baseline tumor assessment will be censored at the date of the first administration of IMP (Day 1).

3.3.2.1.2 Disease control rate

The disease control rate is estimated by dividing the number of participants with disease control (confirmed CR, PR or SD as BOR according to RECIST v1.1) by the number of participants from the analysis population.

3.3.2.1.3 Duration of response

The duration of response is defined as the time from the date of first initial occurrence of the confirmed CR or PR, to the date of first documentation of objective PD according to RECIST 1.1 (1, 2) definitions or death due to any cause, whichever occurs first.

For participants with ongoing response at the time of the analysis cut-off date or at the time of initiation of a new anticancer therapy, DOR will be censored at the date of the last evaluable tumor assessment (not showing documented progression) performed before or on the day of initiation of a new anticancer therapy (if any) or the analysis cut-off date.

3.3.2.2 Main analytical approach

3.3.2.2.1 Progression-free survival

Analysis of PFS will be based on an estimand defined according to the following attributes:

- The endpoint is PFS.
- The treatment condition of interest is tusamitamab ravtansine.
- The analysis population is the all-treated population (defined in Section 2).
- Intercurrent events:
 - The study intervention discontinuation intercurrent event will be handled with the treatment policy strategy. PFS will be assessed based on tumor assessments regardless of study intervention discontinuation.
 - The further anticancer therapy (including further systemic anticancer therapies) intercurrent event will be handled with the hypothetical strategy. PFS will be assessed based on tumor assessments had a further anticancer therapy not being taken. PFS will be assessed based on tumor assessments up to the time of initiation of further anticancer therapy.
 - Two or more consecutive missing/unevaluable tumor assessments immediately before documented PD or death will be handled with the hypothetical strategy. PFS will be assessed based on tumor assessments had 2 consecutive tumor assessments not been missed immediately before documented PD or death. PFS will be assessed based on tumor assessments up to the last evaluable tumor assessment documenting no progression.

- The population-level summary will include:
 - Kaplan-Meier estimates of the 25th, 50th, and 75th percentiles and their associated 95% CIs. The method of Brookmeyer and Crowley and a log log transformation of the survival function will be used to construct 95% CIs.
 - Number (%) of participants at risk as well as the probabilities of being event-free at least at 2, 4, 6, 8, and 10 months with 95% CIs using the Kaplan-Meier method and a log log approach based on a normal approximation following Greenwood's formula.
 - Kaplan-Meier curves including the number of participants at risk at key time points.

In addition, the number (%) of participants with an event and the type of event (documented disease progression or death without documented disease progression) and the number (%) of censored participants and reason for censoring (no baseline tumor assessment, no evaluable postbaseline tumor assessment, alive without documented disease progression, event occurred after 2 or more non-evaluable tumor assessments, or initiation of further anticancer therapy) will be analyzed.

In the absence of documented disease progression or death before the analysis cut-off date (taking into account the intercurrent event handling strategies), PFS will be censored at the date of the last evaluable tumor assessment (not showing documented disease progression) performed before the analysis cut-off date, or at the date of the first administration of IMP (Day 1) if no baseline tumor assessment or no evaluable postbaseline tumor assessment.

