2 ANALYSIS POPULATIONS

The following populations for analyses are defined:

Population	Description	
Pre-screened	All participants who signed the pre-screening informed consent.	
Screened	All participants who signed the screening informed consent for study participation	
Enrolled	All participants from screened population who have been allocated to intervention regardless of whether the intervention was received or not.	
All-treated	All enrolled participants exposed to the study treatment, regardless of the amount of treatment administered. All safety analyses will be performed on this population, which is also the primary population for analysis of all efficacy parameters.	
Activity	All-treated participants who have measurable disease at study entry and at least 1 postbaseline evaluable tumor assessment. Participants with no postbaseline evaluable tumor assessment but with an early clinical progression or who died from disease progression will also be included in this set. This population is the secondary population for analysis of efficacy parameters.	
РК	All participants from the all-treated population with at least 1 postbaseline PK concentration with adequate documentation of dosing and sampling dates and times.	
ATA	All participants from the all-treated population with at least 1 postbaseline ATA result (negative, positive, or inconclusive).	
Population without trial impact	All exposed participants:	
(disruption) due to COVID-19	 without any critical or major deviation related to COVID-19 	
	 and who did not permanently discontinue treatment due to COVID-19 	
	 and who did not permanently discontinue study due to COVID-19. 	

Table 3 -	Population	for analyses
-----------	------------	--------------

Abbreviations: ATA = anti-therapeutic antibody; PK = pharmacokinetic.

Note: In practice, a participant will be included in the enrolled population if the question "Will the subject continue in the treatment phase?" has been answered as "Yes" in the "Completion of screening phase" electronic case report form page.

In practice, a participant will be included in the enrolled population if the question "Will the subject continue in the treatment phase?" has been answered as "Yes" in the "Completion of screening phase" electronic case report form page.

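### PFS censors at Day 1 any participant with early clinical progression, no evaluable post-baseline scan and no counted death; this can only raise the curve relative to counting them as early events, and no supplementary PFS analysis shows by how much

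*SAP*

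**What the plan says.** SAP 3.3.2.1.1 measures PFS from first dose "to the date of the first documentation of objective PD according to RECIST v1.1 (1, 2) or death due to any cause". Clinical progression is not an event, and section 3.3.2.2.1 does not name it as an intercurrent event. The analysis population is all treated participants.

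Two passages set the Day 1 rule. In 3.3.2.1.1: "A participant without PFS event (documented disease progression or death) and without any evaluable post-baseline tumor assessment will be censored at the date" of first dosing. In 3.3.2.2.1, participants with no counted event are censored at the last evaluable scan, "or at the date of the first administration of IMP (Day 1) if no baseline tumor assessment or no evaluable postbaseline tumor assessment". Protocol 9.2.3.1 has the same rule.

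Two hypothetical strategies in 3.3.2.2.1 decide which deaths count. For death or progression after two or more consecutive missed scans, "PFS will be assessed based on tumor assessments up to the last evaluable tumor assessment documenting no progression". For new anticancer therapy, only assessments up to its start are used.

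The plan expects participants who deteriorate before a scan. SAP section 2 says of the activity population: "Participants with no postbaseline evaluable tumor assessment but with an early clinical progression or who died from disease progression will also be included". SAP section 4 counts them toward the 38 evaluable. SAP 3.2.2 and 3.3.2.2.2 keep them in the ORR and DCR denominators as non-responders.

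SAP 3.2.3, under the primary endpoint, states: "No sensitivity analysis is planned in this study". ORR and DCR each have a supplementary analysis. None is listed for PFS.

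**The concern.** A participant censored at Day 1 leaves before the first Kaplan-Meier risk set and adds nothing to the curve. That is harmless if the scan is missing for unrelated reasons. It is not harmless if the scan is missing because the participant declined quickly, since the method then assumes that this participant's prospects match those of participants who were scanned.

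Counting deaths solves only part of this. A death soon after clinical progression is an event. A death after two or more missed scans, or after new therapy, is set aside by the hypothetical strategies. With no evaluable post-baseline scan to fall back on, the only rule left sends the participant to Day 1.

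What is at stake is the description of early PFS, above all the 2- and 4-month rates, in a single-arm study with no internal comparison.

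**Working it through.** **Inputs from the documents**
- N = 38 treated (SAP section 4). The plan's funnel reproduces: 285 × 0.16 × 0.85 = 38.8; in reverse, 38/(0.16 × 0.85) = 279.4, against about 285 stated.
- First scan at 8 weeks (Protocol 8.1). Landmarks at 2, 4, 6, 8 and 10 months (SAP 3.3.2.2.1).
- A month is 30.4375 days (SAP 5.4.1), so 2 months = 8.70 weeks and 4 months = 17.39 weeks.

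The documents give no PFS median, rate or event count, so there is no plan figure for PFS to reproduce.

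**Assumptions**
- k participants have clinical progression before the first landmark, no evaluable scan and no counted death. k is not given; 0 to 6 is shown.
- PFS in the other 38-k is exponential with a median of 24 weeks. This borrows the expected median treatment duration (SAP 1.1) as a proxy. Medians of 16 and 12 weeks were also run.

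**Formulas**
- As planned: S_plan(t) = S_scanned(t) = 0.5^(t/24), with t in weeks.
- With the k counted as events before the landmark: S_alt(t) = [(38-k)/38] × S_scanned(t).
- Overstatement of a landmark rate: S_plan/S_alt = 38/(38-k). This ratio does not depend on the assumed median.
- Median with the k counted: 24 × [1 + log2((38-k)/38)] weeks.

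| k | factor | 2-month PFS | 4-month PFS | median (months) |
|---|---|---|---|---|
| 0 (as planned, any k) | 1.00 | 77.8% | 60.5% | 5.5 |
| 1 counted | 1.03 | 75.7% | 58.9% | 5.3 |
| 2 counted | 1.06 | 73.7% | 57.3% | 5.1 |
| 4 counted | 1.12 | 69.6% | 54.1% | 4.6 |
| 6 counted | 1.19 | 65.5% | 51.0% | 4.1 |

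At k=4 with a 16-week median, the planned 68.6% and 47.1% become 61.4% and 42.1%. With a 12-week median, 60.5% and 36.6% become 54.1% and 32.8%.

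**Check by simulation.** Settings: 24-week median, progression seen at the next 8-weekly scan, clinical progression at weeks 2 to 8, k=4.
- None of the k dies early: 2-month PFS 79% as planned against 71% with the k counted; 4-month 63% against 57%; median about 27.6 against 23.9 weeks.
- Each of the k has a 50% chance of dying within 8 weeks of clinical progression, which counts as an event: 78% against 71%; 60% against 56%; 26.2 against 23.8 weeks.

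The gap shrinks when some of the k die early, but keeps its direction.

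**The case against.** The strongest reply is that the main analysis is conventional and its rules agree with each other. PFS is defined on objective progression or death, and Protocol 10.12 says that symptomatic deterioration does not describe objective response. A reader might infer that the plan calls these participants treatment failures and then contradicts itself by censoring them. The documents do not support that. Their terms are evaluable and non-responder, and non-responder is the default for anyone without a confirmed response, whatever the reason.

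The plan also limits the group. Protocol 8.1 asks for an end-of-treatment scan if there was no imaging in the past 4 weeks, and for 12-weekly scans after stopping without documented progression. Protocol 10.12 asks for every effort to document progression after stopping. SAP 5.4 uses unscheduled scans. Protocol 4.1 places the end-of-treatment visit before any new therapy. A narrow gap remains. Baseline imaging may be up to 28 days before Day 1, so a participant who stops after one dose and switches quickly may need no end-of-treatment scan, and scanning ends at new therapy.

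A reader might also infer that the curve describes only participants fit enough to be scanned. It does not: death without documented progression is an event even in someone never scanned, unless it follows two or more missed scans or new therapy.

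The size is unknown, and large k is demanding. If 24 weeks is taken as the true all-treated median, 38 × (1 - 0.5^(8/24)) = 7.8 participants fail before week 8 from all causes, so k=4 would be 4/7.8 = 51% of them. Sampling error is larger than the shift: in that model the median of 38 uncensored times ranges from about 15 to 37 weeks.

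Lastly, SAP 3.3.2.2.1 already tabulates censoring by reason. That shows part of k. However, the listed reasons do not separate clinical progression from withdrawal, and Day 1 censorings can fall under several headings.

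These points make the issue smaller. They leave the direction of the effect and the absence of a supplementary PFS analysis as they were.

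**Conclusion.** The point holds as a limited one. Day 1 censoring of clinical progressors with no evaluable scan and no counted death is likely informative. Relative to counting them as early events, it can only raise the PFS curve. With N=38 the landmark rates are overstated by 38/(38-k): nothing at k=0, 3% at k=1, 12% at k=4. With a 24-week median in scanned participants, k=1 to 6 means about 2 to 12 percentage points at 2 months, 2 to 10 at 4 months, and 0.2 to 1.4 months in the median. These figures assume that all k progress before the first landmark and none has a counted death; counted early deaths reduce them.

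The documents do not support saying that PFS will be inflated by a particular amount, because k is not given and may be zero. Nor do they make RECIST-only PFS a wrong main analysis. PFS is a descriptive secondary endpoint in a study that tests no hypothesis, and ORR and the interim rule do not change. The point justifies a low-cost addition to the SAP and leaves the endpoint as defined.

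**What to change.** Leave the RECIST-only PFS in SAP 3.3.2.2.1 as the main analysis. Add one supplementary PFS analysis on the all-treated population. For participants without documented RECIST progression:
- investigator-recorded early clinical progression, as used for the activity population, is an event on its date;
- death from any cause is an event on its date, including after missed scans, after new anticancer therapy, or with no post-baseline scan.

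Report its median and landmark rates beside the main result. Give the number censored at Day 1 in the main analysis, split by underlying reason: clinical progression, new therapy, withdrawal, other.

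**Cost.** SAP wording and one Kaplan-Meier table. The documents give no definition or dating rule for early clinical progression, so a short one is needed. Building the activity population already requires these participants to be identified, but the sponsor should confirm that the date is recorded.

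**Downside.** Clinical progression is less objective than RECIST progression. The supplementary analysis also targets a different estimand, because counting deaths after missed scans or new therapy reverses two of the main intercurrent-event strategies. A difference between the two results would therefore reflect more than the Day 1 rule, and the Day 1 counts by reason are needed to interpret it. If nobody is affected, the two analyses agree.
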